2.3.2 KNOWN POTENTIAL BENEFITS

There are no direct benefits to study participants related to their enrollment in the proposed research. They may, however, benefit from the health and risk prevention information and written materials that they receive as intervention participants concerning HIV risk-reduction or healthier living. Network members may potentially benefit from health-related information disseminated by intervention participants. All participants will also have the opportunity to receive free HIV/HCV counseling and testing, and linkage to care through the diaspora organization.

- Autonomous NGO "Scientific and Educational Center "Most v budushee" (Bridge to the future) IRB#1 (00010190) in Russia

(2) Referral for medical or psychological treatment as the result of study participation if needed: The project team works closely with the Tajik Union in Moscow as an NGO that advocates and represents the interests of Tajiks in the Russian diaspora including their legal problems related to drug use or other illegal activities. The Union will arrange referral of services for participants who (if any) experience legal problems related to drug use or undue psychological stress due to their participation in the study. Participants who report recent thoughts of self-harm or suicidal ideation during an interview will be referred to the Union for assistance in accessing mental health services.

(3) HIV/HCV rapid testing will be voluntary and sharing results with the research will be optional.

Participants who receive a positive confirmatory test will be referred to the Tajik Union for assistance in accessing follow-up services in Moscow through the Volunteer Doctors Association or linkage to care in Tajikistan.

(4) Procedures for Research Team Management of AEs, SAEs and Other Study Risks: All research staff and session facilitators will be trained in how to recognize and appropriately respond to both an adverse event (AE) and a serious adverse event (SAE) should one should occur as part of the study. Staff members will be instructed that such events or incidents must be reported immediately to the Moscow site coordinator and documented using a specially prepared project form, and then reported within 24 hours to Drs. [name] and [name]. They, in turn, will inform the NIH funding agency and also the IRBs of the University of Illinois at Chicago (FWA00000083), PRIZMA Research Center (FWA00017140), and the Scientific and Educational Center in Moscow (IRB #00010190). Further action will be taken under the advisory guidance of the three IRBs and NIH. (See also below for further details on actions to be taken with a possible breach of confidentiality.)

(5) At subway stops where on-duty Moscow police are known to stop and check the documents of passengers with non-Slavic (Russian) appearance, group facilitators will accompany intervention participants to and from the station to the PRIZMA office for the group sessions.

(6) Strategies to protect privacy and confidentiality:

- a. Intervention sessions will be held at the PRIZMA Satellite Office. The PRIZMA office conducts a variety of activities unrelated to injection drug use; visiting the office will not place participants at risk of being identified as a drug user.
- b. Interviews will be held at the PRIZMA Satellite Office or a location selected by the participant that is sufficiently private that his answers cannot be overheard.
- c. To protect the confidentiality of data, questionnaires will not include personal identifiers. A research ID number will be assigned to each participant. A project tracking database in REDCap will record participants' names and project-assigned anonymous ID numbers for follow-up purposes. The log will be used to contact participants for follow-up interviews. It also will be used by [name] to assure that participants' anonymous ID numbers are entered consistently across interview data points, and during coding to link the anonymous ID number of each intervention participant with the anonymous number of each of their 2 network recruits in examining network diffusion. No names or personal identifiers, however, will ever appear on the study's questionnaires, in the project data set, or other project material. The tracking data will be destroyed when primary data analysis has been completed.
- d. Test results will be stored in a secure REDCap database separate from interviews and other study data. Participants will be assigned a testing code number that is separate from their research ID number used to identify interviews. A list of matching identifiers will be kept in REDCap. Only the PI, the Moscow site PI, the Moscow Project Coordinator, and the data coordinator will have access to this list.
- e. When study participants are referred to the Tajik Union for assistance with legal, health, or mental health issues, no personal information will be disclosed to Union staff, including information regarding their substance use or HIV or hepatitis C status.
- f. All publications resulting from the study will appear without participant names or information that would identify them.
- g. NIH Certificate of Confidentiality: We will not apply for an NIH Certificate of Confidentiality that protects against disclosure of personally identifiable information in the U.S. as this legal document has no legal status in Russia or Tajikistan.
- h. Protection of Data: Data collected on tablets with the Qualtrics offline mobile app will be uploaded to the secure web-based platform whenever a network connection is available. Process data will be entered into a secure REDCap database hosted at UIC. Participant tracking data will be stored in a locked file at the PRIZMA Moscow office to which only the Moscow Site PI ([name]), Moscow Project Coordinator ([name]) and the senior interviewer/data coordinator (TBA) will have access. Test results will be stored in a secure REDCap database to which only the investigators and key personnel with a valid user ID will have access. Test results will be recorded with different identifiers than interview data, and a list of matching interview and test result identifiers will be kept in REDCap. Data collected on laptop computers or tablets will be deleted after being transferred to the central repository. Laptops will have whole drive encryption enabled and will be kept in a locked storage cabinet when not in use. Data will not be stored on removable devices.

Completed audio recordings will be kept with only code numbers (no names or other identifiers) in secure Box Health Data folder and destroyed six months after being transcribed.

Data transfers to UIC will include only de-identified data and will be carried out by [name] or [name] using the UIC Box service. This is the university-approved method for secure file sharing outside of the university network. The PI will set up a secure folder with restricted access for file transfers.

i. Should any breach of confidentiality occur five steps will be taken. First, the participant will be informed as to the nature of the breach, and its possible ramifications. Second, the Investigators will immediately notify the IRBs of the University of Illinois at Chicago (FWA00000083), PRIZMA Research Center (FWA00017140), and the Scientific and Educational Center in Moscow (IRB #00010190) and the project's NIH funding agency. Third, the Investigators will review existing confidentiality safeguards to determine why and how the breach occurred. Fourth, the PIs will halt client intake until such time that the IRBs can review existing procedures as to their quality and completeness. Finally, appropriate steps will be taken as determined by the 3 IRBs and approved by NIH. The participant also will be referred if needed to the Tajik Union for legal support and/or referral to appropriate service providers or other relevant organizations. The Union has agreed to accept this role.

(7) COVID-19 mitigation procedures

- a. Masks will be required during group activities and face-to-face interviews.
- b. Physical distancing will be employed during group activities and face-to-face interviews
- c. Equipment (e.g. tablet computers) will be disinfected between uses

Other safety procedures include participant temperature checks before entry into the intervention or interview room, hand sanitizer will be supplied at intervals within the project area, the intervention and interview rooms will be disinfected after each use, interviews will be scheduled with sufficient time between participants to allow for disinfectant of contact areas, staff will have a check-list of safety procedures to follow with each eligibility screening, intervention session, and interview.

3 OBJECTIVES AND ENDPOINTS

OBJECTIVES	ENDPOINTS	JUSTIFICATION FOR ENDPOINTS	PUTATIVE MECHANISMS OF ACTION
Primary			
Assess the efficacy of the MASLIHAT intervention compared to the TANSIHAT control condition for reducing injection equipment sharing, condomless sex, and heavy alcohol use among intervention participants and among their network members.	Reduce the proportion of men sharing syringes or other injection equipment in the past 3 months to 10% or less; reduce the proportion of men engaging in condomless sex in the past 3 months to 10% or less. Reduce the proportion of men engaging in heavy	Behavioral outcomes are predictive of HIV and hepatitis C infection. Sharing of syringes and other injection equipment is a significant risk factor for HIV and HCV, and condomless sex is a significant risk factor for HIV. Heavy alcohol use increases the	MASLIHAT is a peer education network intervention based on social cognitive theory which suggests that individuals will adopt new norms and practices that reduce their HIV risk by learning how and why they should do so and by observing role

OBJECTIVES	ENDPOINTS	JUSTIFICATION FOR ENDPOINTS	PUTATIVE MECHANISMS OF ACTION
	alcohol use in the past 3 months to 10% or less.	likelihood of risky behavior that leads to infection acquisition, and increases the risk of liver disease associated with HCV.	models to follow. We also draw on Yang's Theory of Migration, which posits that successfully changing risk behavior requires modifying the psycho-social conditions and life circumstance that help to generate it. By transforming their own HIV norms and behavior, and encouraging others at risk to do so too, migrant peer educators can initiate positive changes at the individual and social network levels in both their host country and their home country when they return.
Secondary			
Assess the efficacy of the MASLIHAT intervention compared to the TANSIHAT control condition for reducing the incidence of HIV and hepatitis C infection among intervention participants and among their network members .	Reduce the 12-month incidence of HIV and HCV by 50% compared to the control group.	The risk of HIV and HCV infection will be reduced by changes in individual and peer network behavior.	
Tertiary/Exploratory			
Assess network penetration and diffusion among networks of MASLIHAT participants.	80% of MASLIHAT participant network members report conversations about syringe cleaning, condom use, etc.	The MASLIHAT intervention teaches participants to engage in peer education activities	

OBJECTIVES	ENDPOINTS	JUSTIFICATION FOR ENDPOINTS	PUTATIVE MECHANISMS OF ACTION

Assess changes in and mediating effects of HIV knowledge, risk awareness, behavioral norms, and self-efficacy among MASLIHAT participants and their network members compared to the TANSIHAT control condition.
 
Assess the mediating and moderating effects of depression and loneliness among MASLIHAT participants and their network members compared to the TANSIHAT control condition.
			
HIV knowledge, risk awareness, behavioral norms, and self-efficacy are theoretical mediators for intervention effects.
 
Depression and loneliness are indicators of psycho-social well-being that potentially mediates or moderates intervention effects.

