1 PROTOCOL SUMMARY

1.1 SYNOPSIS

Title:	MASLIHAT Intervention for Tajik Male Migrants Who Inject Drugs
Grant Number:	1R01DA050464
Study Description:	
This protocol will test the efficacy of the MASLIHAT peer education HIV prevention intervention for Tajik migrant laborers who inject drugs in the host country, against an attention control. The primary outcomes are self-reported risk behaviors among participants and network members over 12 months following the intervention, including syringe sharing, and sex without condom. Follow-up interviews will be conducted at 3, 6, 9, and 12 months. We will conduct HIV testing at baseline and 12-month follow-up, and HCV testing at baseline and 6- and 12-month follow-up. We expect the MASLIHAT intervention to be associated with greater reduction in injection and sexual risk behavior during follow-up compared with the control condition.

Objectives[*]:	
Primary Objective: Assess the efficacy of the MASLIHAT intervention compared to the TANSIHAT control condition for reducing injection equipment sharing, condomless sex, and heavy alcohol use among intervention participants and among their network members.
 
Secondary Objectives: Assess the efficacy of the MASLIHAT intervention compared to the TANSIHAT control condition for reducing the incidence of HIV and hepatitis C infection among intervention participants and among their network members

Endpoints[*]:	
Primary Endpoint: Reduce the proportion of men sharing syringes or other injection equipment in the past 3 months to 10% or less; reduce the proportion of men engaging in condomless sex in the past 3 months to 10% or less. Reduce the proportion of men engaging in heavy alcohol use in the past 3 months to 10% or less.
 
Secondary Endpoints: Reduce the 12-month incidence of HIV and HCV by 50% compared to the control group.
 
We will enroll a total of 420 male Tajik migrant workers who inject drugs in Moscow, including 140 intervention participants (70 MASLIHAT, 70 control group) and 280 network members recruited by the intervention participants for participation in the assessments.

Phase[*] or Stage:	Phase 2
Description of Sites/Facilities Enrolling Participants:	Participants will be enrolled at PRIZMA Research Center in Moscow, Russia.

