6.3 MEASURES TO MINIMIZE BIAS: RANDOMIZATION AND BLINDING

The 12 recruitment sites will be pair matched and randomly assigned to a study arm. One of each pair will be assigned to MASLIHAT and the other to the control condition. [name] will create the matched pairs based on site characteristics, and randomization will be determined by the PI using a random number generator. A random number will be generated for each site, and within each matched pair, the site with the smaller number will be assigned to MASLIHAT. To minimize bias during recruitment, site assignments will be masked from project staff engaged in recruitment. The PI will inform the Moscow project coordinator of the site assignment as needed for group scheduling, after the first cohort of participants has been filled for the site. Participants will be informed of their assignment at the time of scheduling the group sessions. [name] will also have access to this information as needed, after recruitment activities are underway. Interviewers will be blinded to site assignment, and the same interview instrument will be used for MASLIHAT and control condition participants. Session facilitators, who may become aware of the recruitment sites from which participants originated, will be instructed during training not to reveal this information to interviewers. Intentional or unintentional breaking of the blind is to be reported to the PI.

The randomization codes will be kept in a password-protected file accessible to the PI, co-investigators, the project coordinator, and the data manager. When preparing data for analysis, the data manager will

blind code recruitment site and study arm. Masking will be removed for reporting interim results to the DSMB.

In addition, we will adopt a position of clinical equipoise. Intervention facilitators and interviewers will be informed that we are testing two different interventions, but neither is assumed to be superior to the other. Facilitators will be assigned to one or the other, while interviewers will be blinded to participant condition. Data collection will be conducted by interviewers who are not involved in intervention delivery. Interviews will be standardized using a computer-assisted instrument, and sensitive sections will be self-administered.

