Interviews: Intervention participants and network members will complete computer-assisted personal interviews (CAPI) at baseline (prior to first intervention session), and at 3, 6, 9, and 12 months post-intervention. All baseline and 12-month interviews will be conducted in a private room at the PRIZMA office; intermediate follow-up interviews may be conducted at the PRIZMA office or at a location selected by the subject. Trained interviewers will administer the 60 to 90-minute questionnaire, using a computer-assisted personal interview (CAPI) system (Qualtrics) to record responses. For the more sensitive questions such as sexual behavior and STIs, the interviewer will instruct the participant to enter his responses. The CAPI system will ensure proper administration of skip sequences. For quality control purposes, 20% of interviews will be randomly selected to be audiotaped, and half of these audiotapes will be reviewed by [name] or [name] for quality assurance. Using electronic data capture and requiring timely data uploads will allow the data manager to monitor research progress and conduct quality control checks. The questionnaires were developed and tested with members of the population using cognitive interviewing (CI).⁶² Translations were validated using "back translation" with a member of the study population.

Self-report Measures

Background measures. The baseline interview includes measures of basic sociodemographic variables (education, marital status, migration history, religion), community involvement/social activities, and health (general health, STIs). The follow-up interviews also collect self-reported STIs since last interview.

Outcome measures. Primary outcome measures are syringe sharing in the past 3 months, and vaginal or anal sex without a condom in the past 3 months. Other measures include syringe cleaning methods, and the Alcohol Use Disorder Identification Test (AUDIT)⁶³ to assess alcohol consumption and alcohol-related problems at each time point.

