Theoretical mediators. In addition to risk behavior, the questionnaire will assess theoretical mediators including HIV knowledge, risk awareness, behavioral norms, self-efficacy, depression, and loneliness. HIV knowledge is assessed with 16 true/false items; risk awareness is assessed with questions such as "How likely are you to get HIV?" and "How much do worry about HIV?" Behavioral norms⁶⁴⁻⁶⁶ will be assessed with questions such as "How many of your friends who shoot drugs use a needle after someone else, without bleaching or cleaning?" (descriptive norms), and "How many of your friends would disapprove if you shared a needle with a stranger?" (injunctive norms). Responses are given on a 5-point scale from 1 (none) to 5 (all). Self-efficacy for safer drug injection will be measured with six items adapted from the CIDUS-III study⁶⁷ (e.g., "I can avoid sharing a needle even if I am dope sick or in withdrawal"), rated on a four-point scale from "strongly agree" to "strongly disagree". Depression will be measured using the Centers for Epidemiological Studies Depression Scale -- Revised (CESD-R)⁶⁸, and loneliness will be measured using the UCLA Loneliness Scale⁶⁹.

Network penetration & diffusion. Diffusion of MASLIHAT messaging/norms at the network level will be assessed using measures successfully used by SHIELD and other public opinion leadership interventions such as asking network members as to how many (if any) MASLIHAT peer educators they know, whether anyone within their drug using network talked with them about HIV since they were last interviewed, and whether they talked about specific topics (e.g. condom use, syringe cleaning, HIV testing).

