9.4.2 ANALYSIS OF THE PRIMARY ENDPOINT(S)

Relative frequency of syringe sharing, equipment sharing, and vaginal or anal sex without a condom in the past 3 months will be measured at each time point on a 7-point Likert-type scale (Never, Rarely, Less than half the time, About half the time, More than half the time, Most of the time, Always). We will analyze ordinal outcomes, and we will also dichotomize responses to analyze binary (none/any) outcomes.

We will conduct repeated measures mixed effects regressions with random intercepts for subject and recruitment site to test the effect of intervention condition on changes in the outcome variables. We will use ordinal logistic regression for ordinal outcomes and modified Poisson regression for binary outcomes. We will conduct a test of the proportional odds assumption with a likelihood ratio test comparing the proportional odds model with a non-proportional odds model.⁷⁴ We will include the interaction of time and participant type (intervention participant vs. network member) to test for differential effects. If the interaction term suggests differential effects ($p < .10$), we will stratify analyses by participant type. Sociodemographic characteristics (age, education, time in Moscow) will be included as covariates in the analysis if they are related to the outcome at baseline or if they vary significantly across conditions. All participants with at least one follow-up interview will be included in the analysis.

Dosage: If there is variability in attendance, we will estimate repeated measures mixed effect models predicting outcomes with session attendance and the interaction between time, intervention condition, and session attendance as predictors. A significant interaction effect will indicate that the effect of the intervention is moderated by session attendance.

Social Network Diffusion. Additional analyses among network members will examine associations between exposure to intervention concepts (i.e. conversations about health, drugs/alcohol HIV) and changes in outcomes over time.

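### The exploratory diffusion endpoint is a one-arm 80% target with no control comparison, and the plan states no check for contamination

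*Combined protocol and SAP*

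**What the plan says.** The exploratory objective in Section 3 is limited to one arm: "Assess network penetration and diffusion among networks of MASLIHAT participants". Its endpoint is "80% of MASLIHAT participant network members report conversations about syringe cleaning, condom use, etc". No visit, test, interval or rule for combining topics is given. The two exploratory objectives that follow, on mediators and on depression and loneliness, are both framed against the TANSIHAT control.

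The data are not limited to one arm. Section 8.1 states that "Intervention participants and network members will complete computer-assisted personal interviews (CAPI) at baseline" and at 3, 6, 9 and 12 months. Section 6.3 adds that "the same interview instrument will be used for MASLIHAT and control condition participants", with interviewers blinded. The diffusion items in 8.1 ask network members "how many (if any) MASLIHAT peer educators they know, whether anyone within their drug using network talked with them about HIV", and then which topics were discussed, for example condom use, syringe cleaning and HIV testing.

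Section 9.4.2 contains the only analysis labelled as diffusion: "Additional analyses among network members will examine associations between exposure to intervention concepts" and changes in outcome. It mentions no contrast between arms. Section 4.2 says that sites are randomised so that the control group is not contaminated. No analysis section returns to that threat.

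**The concern.** A one-arm rate shows how common these conversations are in MASLIHAT networks, but not how common they would have been without MASLIHAT. Background talk is plausible in both arms. The item asks "whether anyone within their drug using network talked with them about HIV since they were last interviewed", so each recall window opens just after a 60 to 90 minute interview that covers HIV knowledge, injection norms and self-efficacy. Men in both arms are also referred for HIV and HCV counselling and testing, and network members must see their index man at least weekly (Section 5.1). How much talk this prompts is unknown.

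Contamination also has possible routes. Network members are chosen by contact with the index man and need not come from his recruitment site. The two sites being recruited at any time belong to different arms (5.5). Both programmes meet at PRIZMA (6.1.2).

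At stake is the interpretation of the result. If the arms do not differ on behaviour, conversation rates by arm and a contamination indicator would help to separate weak delivery, spill-over and an ineffective message. The plan does not commit to producing either.

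**Working it through.** The 80% is a target, not a calculated figure. The documents give it no sample size, power or background rate, so there is nothing to reproduce. The check has two steps.

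**1. Does the endpoint depend on the control rate?**

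- Network members (Section 1.1): "280 network members recruited by the intervention participants for participation in the assessments". With two per index man and 70 index men per arm, 70 × 2 = 140 per arm, and 2 × 140 = 280 agrees with the total.
- After the 15% attrition allowed in 9.2: 140 × 0.85 = 119 per arm.
- Sites: 12, so 6 per arm (6.3). Network members per site: 119 / 6 = 19.8.

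The target is met at 80% in MASLIHAT networks whatever happens in control networks. The implied arm difference is 80 minus the control rate. That rate is assumed here, from 20% to 80%.

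**2. Would a between-arm comparison be informative with these numbers?**

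The intracluster correlation (ICC) of 0.05 is borrowed from the behavioural outcomes in 9.2; 0.10 is a sensitivity value.

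- Design effect = 1 + (19.8 − 1) × 0.05 = 1.94; effective n = 119 / 1.94 ≈ 61 per arm.
- At ICC 0.10: design effect 2.88, effective n about 41.
- Standard error of the difference = √[(0.8 × 0.2 + pc(1 − pc)) / effective n], where pc is the control rate. The interval uses t on 10 degrees of freedom.
- Power is a normal approximation on the effective n at ICC 0.05, two-sided.

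| Assumed control rate | Difference (points) | 95% CI, ICC 0.05 | 95% CI, ICC 0.10 | Power, alpha 0.05 | Power, alpha 0.01 |
|---|---|---|---|---|---|
| 20% | 60 | 44 to 76 | 40 to 80 | >0.99 | >0.99 |
| 40% | 40 | 22 to 58 | 18 to 62 | 0.997 | 0.98 |
| 50% | 30 | 12 to 48 | 8 to 52 | 0.95 | 0.83 |
| 60% | 20 | 2 to 38 | −2 to 42 | 0.68 | 0.44 |
| 70% | 10 | −7 to 27 | −11 to 31 | 0.25 | 0.10 |
| 80% | 0 | −16 to 16 | −20 to 20 | – | – |

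All six rows meet the stated endpoint. The comparison would detect a difference of 30 points or more with good power at ICC 0.05, and would be imprecise for differences of 20 points or less. The one-arm rate is itself imprecise: an observed 80% of 119 has a 95% interval of about 67% to 93% at ICC 0.05 (t on 5 degrees of freedom).

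**The case against.** The strongest reply is that the 80% is a reach benchmark. Its justification in Section 3 is that MASLIHAT trains men to do peer education, and, like the attendance thresholds in 4.3, it asks whether delivery reached its target. It is exploratory and does not itself claim attribution. This stands, and is why the 80% should be kept as a descriptive figure. It does not supply the comparison that attribution would need.

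Three stronger readings are tempting, and the documents do not support them.

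- **That no planned analysis uses the control networks' answers.** The diffusion analysis in 9.4.2 covers network members without restriction to MASLIHAT, so it may include both arms. Section 9.4.1 plans to test the effect of condition on mediators. Section 9.4.9 lists social network interactions among the possible mediators, which could imply an arm contrast. That variable is undefined, does not appear among the mediators in 8.1, and is not linked to the 80% endpoint. The accurate statement is that no such contrast is explicit.
- **That the control-arm conversation rate measures contamination.** It mixes background talk, interview-prompted talk and spill-over. The item on MASLIHAT peer educators known is more specific.
- **That the trial cannot test whether peer educators change their networks.** The randomised comparison of network members' behaviour (9.1) tests this, and does not depend on the 80%.

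It is also fair to say that the control rates above are assumed, and that nothing in the plan forbids reporting these items by arm afterwards. Prespecification would still make the comparison more credible.

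**Conclusion.** The point holds as a gap in an exploratory endpoint. An 80% result would be consistent with an arm difference anywhere from 60 points to none over the assumed control range, so it cannot be attributed to diffusion of MASLIHAT. No section explicitly plans a between-arm comparison of the conversation items or any check for contamination. The randomised primary analysis stands as planned.

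The conclusion rests on one inference: that control network members answer the diffusion items. The questionnaire is not in the documents, but a single instrument with blinded interviewers makes this sound. The absence of a comparator can be read directly from Section 3. The intervals and power rest on the borrowed ICC and the assumed control rates, and ignore the pair matching of sites. They show feasibility only.

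**What to change.** In Section 3 and the SAP:

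1. Keep 80% as a descriptive reach benchmark for MASLIHAT networks, stating the visit and the rule for combining topics.
2. Add, as the diffusion endpoint, the between-arm difference in the proportion of network members reporting conversations on syringe cleaning, condom use and HIV testing at each follow-up, with clustering by recruitment site accounted for. Leave general health and alcohol out of this measure: TANSIHAT addresses both and encourages men to pass on what they learn.
3. Report the number of MASLIHAT peer educators known to control-arm network members, by site and visit, as the main contamination indicator. Knowing a peer educator shows the opportunity for spill-over, not its effect.
4. Show control-arm conversation rates alongside, labelled as background plus possible spill-over and not as contamination itself.

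This needs no new items for network members or index men. Section 9.1 places the formal SAP before the first interim analysis of 3-month outcomes, which is a natural point to prespecify it. The cost is wording in two places, one extra table, and a diffusion claim that is harder to make.
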